11.3. VITAL SIGNS

Vital sign measurements of Systolic Blood Pressure, Diastolic Blood Pressure, Heart Rate and Respiratory Rate (absolute and change from baseline as appropriate) will be summarized at

each timepoint (Screening [supine], Baseline [Day 1], Week 1 [Day 8], Week 2 [Day 15], Week 3 [Day 22], Week 4 [Day 29], Week 6 [Day 43], Week 8 [Day 57] and at Day 57 [or early termination]). Temperature will be summarized in similar fashion at Screening and Day 57 (or early termination).

For vital signs, abnormal values will be identified as those outside (above or below) the reference ranges that are defined in Table 6.

Table 6. Reference Range for Vital Sign Values

Vital Sign Parameter	Range
Systolic blood pressure	100–140 mmHg
Diastolic blood pressure	60–90 mmHg
Respiratory rate	12–20 breaths per minute
Heart rate	60–100 beats per minute
Temperature	36.8°C–38.3°C

All vital sign values collected after the Baseline dose of study drug will be evaluated for clinically notable results using the criteria presented in Table 7. A listing of all subjects with at least one clinically notable vital sign value will be prepared; for a given subject, this listing will not only include flagged vital sign parameters, but will present the results of all scheduled and unscheduled vital sign evaluations for the patient. A summary table of the incidence of clinically notable vital signs may be presented.

Table 7. Criteria Used to Identify Clinically Notable Vital Sign Abnormalities

Vital Sign Parameter	Value	Change From Baseline ^a
Systolic blood pressure	≥180 mm Hg	Increase of ≥20 mm Hg
	≤90 mm Hg	Decrease of ≥20 mm Hg
Diastolic blood pressure	≥105 mm Hg	Increase of ≥15 mm Hg
	≤50 mm Hg	Decrease of ≥15 mm Hg
Heart rate	≥120 bpm	Increase of ≥15 bpm
	≤50 bpm	Decrease of ≥15 bpm
Respiratory rate	<12 breaths per minute	—
	> 20 breaths per minute	—

^a Both value and change from baseline criteria must be met to qualify as a clinically notable abnormality.

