9.1.4.2 Day 57 (Visit 8) or Early Termination

Patients will return to the clinic on Day 57 (± 2 days) (Visit 8) or upon early termination from the study. The following procedures will be performed:

- 1. Collect the bottle of study medication, whether partly used, unused, or empty.
- 2. Perform drug accountability.
- 3. Record any changes in current therapies (e.g., prescription and non-prescription medications).
- 4. Assess vital signs (including body temperature).
- 5. Perform physical examination and record any changes from Screening.
- 6. Perform a 12-lead ECG.
- 7. Assess and record AEs occurring since the last evaluation.
- 8. Perform WOMAC.
- 9. Perform the PGIC.
- 10. Collect daily diary (average pain intensity NRS scores, use of study drug and rescue medication).
- 11. Obtain a blood sample for clinical laboratory evaluations and serum sodium measurement.
- 12. Schedule Visit 9 (Follow-up Visit; 7 to 10 days after last dose) and instruct the patient to resume pain medications as needed.

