9.1.5 Follow-Up Evaluation (Visit 9)

At 7 to 10 days after the last dose of study medication, the following procedures will be performed:

- 1. Measure vital signs (blood pressure and heart rate).
- 2. Assess and record AEs occurring since the last evaluation. If any AEs are ongoing at this visit, telephone the patient 30 days after the last dose to assess and record additional updates to these AEs.
- 3. If not collected at Visit 8, collect the bottle of study medication, whether partly used, unused, or empty.

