11.9.4 Vital Signs

Summary statistics will be presented for vital signs and mean changes from baseline to each of the time points. An analysis of abnormal and clinically notable vital sign changes will also be

conducted. Details of these analyses, in particular the definition of abnormal and clinically notable vital signs, will be included in the SAP.

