11.1. ADVERSE EVENTS

Adverse events will be coded using MedDRA. Verbatim description of the adverse events and the MedDRA System Organ Class (SOC) and Preferred Term (PT) for all AEs will be contained in the patient data listings. A separate listing sorted by MedDRA SOC and PT will include all verbatim descriptions associated with each SOC/PT category.

Treatment emergent AEs (TEAEs) will be defined as AEs where onset occurs from the day of first dose of study medication up to and including the 2nd day following the day of last dose of study medication.

All reported AEs (whether treatment-emergent or not) will be included in by-subject AE listings. A separate listing will be created with all the distinct levels of SOC, Preferred Terms and the verbatim investigator description reported in the study. Sorting will be alphabetically by SOC, Preferred Term and then verbatim description.

If the adverse event start date is completely/partially missing, the AE will be considered a TEAE unless the following can be determined:

- The partial AE start date is sufficient to show that the AE started prior to the day of first dose of study drug.
- The AE stop date shows that the AE ended prior to the day of first dose of study drug.
- The partial AE start date is sufficient to show that the AE started after the 2 days following the day of last dose of study drug.

The incidence of TEAEs will be presented using counts and percentages of patients with AEs and tabulated by SOC and PT. SOC will be sorted alphabetically and PT within SOC will be sorted by descending frequency based on the incidence across subjects overall. If a patient has multiple occurrences (start and stop) of an event associated with a specific SOC or PT within a SOC, a patient will only be counted once in the incidence count for the SOC or PT within SOC respectively.

The following specific summary tables will be generated:

- Overall incidence of adverse events
- Incidence of TEAEs by SOC overall and by PT within each SOC
- Incidence of TEAEs related to Treatment by SOC overall and by PT within each SOC
 - If a patient reports two or more adverse events that code to the same PT, the event with the maximum relationship will be included in the table. TEAEs with a missing relationship will be assumed to be treatment related.
- Incidence of TEAEs by Maximum Severity, SOC overall and by PT within each SOC

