Sodium Laboratory Tests

Sodium values (absolute and change from baseline as appropriate) will be summarized at each timepoint (Screening, Baseline [Day 1], Week 1 [Day 8], Week 2 [Day 15], Week 3 [Day 22], Week 4 [Day 29], Week 6 [Day 43], Week 8 [Day 57] and at Day 57 [or early termination]).

The number of patients who meet the important sodium levels (> 146 mmol/L or > 150 mmol/L) anytime between first dose and within 72 hours of final dose of study drug) will be summarized. A patient listing including all sodium test results will be programmed, flagging values that are > 146 mmol/L and > 150 mmol/L. In addition, a listing of patients with at least one sodium result > 150 mmol/L (whether during or after treatment with study drug) will be prepared; this listing will include all sodium test results for the selected patients.

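### The clinically notable vital-sign evaluation has no end of window, so off-drug Follow-Up readings are pooled with on-treatment readings, while the by-visit summary omits that visit

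*SAP*

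**What the plan says.** SAP 11.3 sets the scope of the notable-abnormality evaluation: "All vital sign values collected after the Baseline dose of study drug will be evaluated for clinically notable results". The criteria are in SAP Table 7, and no last day is given. The section commits to a listing of every patient with at least one notable value, showing all of that patient's vital-sign results. It makes the incidence summary optional, although the SAP's list of outputs includes it as Table 14.3.4.9.1.

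Protocol 9.1.5 covers the Follow-Up Visit (Visit 9): "At 7 to 10 days after the last dose of study medication, the following procedures will be performed". The first procedure listed is "Measure vital signs (blood pressure and heart rate"). The vital-signs row of the schedule, in both documents, marks Visit 9. At the preceding visit (Day 57 or early termination), Protocol 9.1.4.2 has the site "instruct the patient to resume pain medications as needed".

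The by-visit summary in SAP 11.3 runs from Screening and ends "Week 6 [Day 43], Week 8 [Day 57] and at Day 57 [or early termination]). Temperature will be summarized"; Follow-Up is not among its time points. Protocol 11.9.4 asks for summary statistics and "mean changes from baseline to each of the time points". SAP section 12 declares a single change from the protocol, which concerns the pain baseline.

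**The concern.** Elsewhere the SAP keeps treatment and post-treatment data apart. Treatment-emergent adverse events run "up to and including the 2nd day following the day of last dose of study medication" (SAP 11.1), and later events have their own table. The sodium threshold counts take values "within 72 hours of final dose of study drug" (SAP 11.2), while a separate listing of high sodium results covers both periods. Concomitant medications are split into during and after treatment (SAP 9.6). The notable vital-sign evaluation has no such split, and nothing in the SAP says that pooling is intended.

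Heart rate and blood pressure matter for this drug. Protocol 4.2 lists sinus tachycardia and hypertension among the related serious events. It links reports of tachycardia to a transient increase in urine output, on average 0 to 12 hours after dosing. A reading a week or more after the last dose says little about that effect and may also reflect resumed analgesics. Such a reading is useful as recovery data, but the by-visit summary, where recovery would be seen, does not include it.

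**Working it through.** The documents give no figure for the vital-sign analysis, so there is none to reproduce. The check is a count of readings, followed by an illustration of scale.

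**1. Readings per patient (schedule of events)**
- A completer has on-treatment post-dose readings at Days 8, 15, 22, 29, 43 and 57, which is 6. Follow-Up makes 7. Off-drug share: 1/7 = 14%.
- A patient who stops after 1 week has 1 reading plus Follow-Up: 1/2 = 50%. After 2 weeks: 1/3 = 33%.

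**2. Is the Follow-Up reading inside the stated window?** It is taken after the Baseline dose, and the window has no end, so yes. It would fall outside the SAP's 2-day window for adverse events and its 72-hour window for sodium, because it is at least 7 days after the last dose.

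**3. Effect on an any-time count with no drug effect.** Assume a notable rate q per reading and independent readings; neither is in the documents. P(at least one in k readings) = 1 − (1 − q)^k.

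| q | k = 6 | k = 7 | rise (points) |
|---|---|---|---|
| 0.5% | 2.96% | 3.45% | 0.49 |
| 1% | 5.85% | 6.79% | 0.94 |
| 2% | 11.42% | 13.19% | 1.77 |
| 5% | 26.49% | 30.17% | 3.68 |

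**4. Effect on the comparison of arms.** Assume 2% per reading on CR845 and 1% on placebo during treatment, and 1% in both arms at Follow-Up.
- Without Follow-Up: CR845 1 − 0.98^6 = 11.416%; placebo 1 − 0.99^6 = 5.852%. Ratio 1.95; difference 5.56 points.
- With Follow-Up: CR845 1 − 0.98^6 × 0.99 = 12.302%; placebo 1 − 0.99^7 = 6.793%. Ratio 1.81; difference 5.51 points.
- Extra patients flagged: 270 × (0.12302 − 0.11416) = 2.4 on CR845 and 135 × (0.06793 − 0.05852) = 1.3 on placebo.

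So the ratio is diluted modestly and the difference is nearly unchanged.

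**The case against.** The strongest reply is that this is an inclusive safety screen with little at stake. The only firm output is a listing in which a Follow-Up value can be recognised by its date. The incidence table is optional in the text, and its shell is in a separate document, so it may already show Follow-Up apart. For blood pressure and heart rate, Table 7 requires both an extreme value and a change (for example, heart rate of at least 120 with a rise of at least 15), so events should be few. Positive correlation within a patient would shrink the rise shown above. An extra reading cannot remove an on-treatment event from an any-time count, and no between-arm test of vital signs is planned. The SAP does not bound everything either: its listing of sodium results above 150 mmol/L covers results after treatment, and Protocol 11.9.1 counts adverse events up to the follow-up visit. The protocol's request for each time point does not name Visit 9, and the full vital-signs listing would show recovery.

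Most of this stands as a limit on size. It does not supply the missing end of window. The sodium example points the other way, since there the count is bounded and only the listing is open. On adverse events the SAP chose a 2-day limit, and Protocol 11.1 gives the SAP primacy.

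A reader might go on to infer that every value after the 2nd day following the last dose should be excluded. The documents do not support that. The early-termination visit is not tied to the date of the last dose, and unscheduled visits may be held for unresolved adverse events (Protocol 9.1.6). A strict cut-off could drop readings from patients who stopped because of an adverse event.

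**Conclusion.** The point holds as a minor but real flaw in a descriptive safety analysis. As written, the rule pools Follow-Up blood pressure and heart rate with on-treatment values, and the same visit is missing from the by-visit summary without being declared as a change. Respiratory rate is less clear: Protocol 9.1.5 does not list it at Visit 9, while SAP 5.2.3 has it at each clinic visit.

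The size is probably small: about 1 to 2 points on the any-time rate at assumed rates of 1% to 2% per reading, with the between-arm difference almost unchanged. Those figures rest on assumed rates and on independence between readings, and serve only for scale. A reader might infer that the pooling would hide a cardiovascular effect of CR845, or that it biases the arms unequally. The first is not supported: even with a doubled on-drug rate, the ratio falls only from 1.95 to 1.81. The second would need the arms to differ in when patients stop treatment, which the documents cannot show. The primary endpoint and the type 1 error rate are not affected.

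**What to change.** - In SAP 11.3 and Table 14.3.4.9.1, report notable abnormalities in two labelled periods. The treatment period runs from first dose through Day 57 or early termination and includes early-termination readings and any unscheduled readings before Follow-Up. The second period is Follow-Up (Visit 9), labelled post-treatment.
- Keep all values in the listing and flag those that are post-treatment.
- Add Follow-Up (Visit 9) as a time point in the by-visit blood pressure and heart rate summaries.

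The cost is SAP wording and one extra column or row. The treatment-period count will hold slightly fewer values, but none are lost: the Follow-Up values move to their own category, and no new data need to be collected.

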11.4. ECGs

Continuous ECG parameters (absolute and change from baseline as appropriate) will be summarized at screening and Day 57 (or early termination). A by-patient listing will also be

prepared, with a separate listing for those patients with a clinically significant abnormal investigator interpretation of ECG results.

12. SUMMARY OF CHANGES FROM PROTOCOL-SPECIFIED ANALYSES

At the time of finalizing this SAP, only the following update has been made in this SAP compared to the Study Protocol V3.0 4th November 2016:

Update 1

Protocol Section 11.7.1 Text:

The baseline score will be calculated as the average of the 4 pain scores collected during the Screening period that qualified the patient for randomization

SAP Section 5.1.1 Text:

The weekly mean pain intensity score will be defined as the sum of non-missing daily "average pain over the last 24 hours" scores reported during that week (Days -7 to -1 [Baseline].... divided by the number of days with non-missing scores for that week.

Reason for update

To ensure the derived baseline derivation of the weekly pain score was equivalent in terms of number of days assessed (i.e. 7 day period using any day with a recorded pain score).

13. REPORTING CONVENTIONS

P-values will be reported to four decimal places; p-values less than 0.0001 will be reported as p<0.0001. The mean and median will be displayed to one decimal place greater than the original value and the measure of variability will be displayed to two decimal places greater than the original value. All statistical programming and analyses will be performed using SAS® (SAS institute, Cary, NC 27513).

The following standards will be used in the data presentation:

- In text tables should be in portrait format, font type would be "Arial" and font size 9 and RTF format. Section 14 tables and figures, and Appendix 16.2 listings should be in landscape format. Output should adhere to US / ICH margins and should not require changes for European page size. For section 14 tables, a blank row will separate the header from the content of the table listing. For tables that have "n (%) only", the placement should be centered below "N=xx" in the column header. Frequency tables will be center justified, and descriptive statistics decimal justified. ICH margins are Top=0.75", Bottom=0.75", Left=1", Right=0.75", Gutter=0", Header=0.6", Footer=0.6", Width=8.27" and Height=11".
- Percentages presented in the in-text tables should be rounded to whole numbers using the SAS rounding function. Percentages presented in Section 14 tables should be rounded to a

single decimal point (xx.x%) using the SAS rounding function. Percentages for values in tables that are <1 should be represented as “<1”. If “%” is part of the column heading, do not repeat the “%” sign in the body of the table. Unless specified otherwise, “%” should reflect the total population of the treatment group(s). Any deviation from that should be part of the footnote. For 0 counts, leave the corresponding percentage blank.

- The format for minimum and maximum should be “Min, Max”. Standard deviation should be the default for representing scale for demographic and baseline characteristics. For tables presenting statistical analyses, the SD will be used unless the standard error has been specified. Standard deviation should be abbreviated as “SD”, and presented within parenthesis next to the mean value, without any +/- sign. The standard deviation should have one additional decimal place beyond that of the mean (eg, mean has one decimal place, SD should have two).
- “N” will represent the entire treatment group, while “n” will represent a subset of the treatment group. For tables with population designated as a row heading, “N” should be used (ie, tables where all participant data is not available for every variable within a treatment group). As a guideline, if the number is used in a denominator it should be presented as “N”. If the number is used in the numerator, it should be presented as an “n”.
- The heading should consist of at least 3 lines. Line 1: Table/Appendix number. Line 2: Protocol identifier / Table Title – Adjunct Description of Table Title (optional). Line 3: Population. The title for in-text tables should begin with the Table/Appendix number.
- A solid line should appear both above and below the column headings of a table. A solid line should appear at the end of the table or at the bottom of each page if the table extends to more than one page. Footnotes should start after the bottom solid line.
- Footnotes should be left-justified at the bottom of the page. Footnotes must be present on the page where they are first referenced. If more than four footnote lines are planned then a cover page may be used to display footnotes.
- The maximum length of a title is 255 characters (including spaces).
- Legends will be used for all figures with more than one variable or item displayed.
- Figures should be generated in black and white. Lines should be wide enough to see the line after the figure has been fotocopied.
- All tables, figures, and data listings will have the name of the program and date/time stamp on the bottom of each output.

All statistics will be validated with two independent programming codes. All tables, figures and listings will be validated by a two-person review of the output.

15. TOCS FOR TABLES, FIGURES, LISTINGS AND OUTPUT

15.1. TABLES

Mock tables are presented in a separate document. The current version based on this SAP are detailed in CLIN2002-PO SAP Table Shells V1_0 18JAN17 and detailed below:

Table 14.1.1.1 Patient Disposition – Screening and Randomization Enrolled Population

Table 14.1.1.2 Patient Disposition Full Analysis Population (FAP)

Table 14.1.1.3 Patient Disposition – Weekly Dose Full Analysis Population (FAP)

Table 14.1.1.4 Patient Disposition – Analysis Populations Full Analysis Population (FAP)

Table 14.1.1.5 Major Protocol Deviations Full Analysis Population (FAP)

Table 14.1.2 Demographic and Baseline Characteristics Full Analysis Population (FAP)

Table 14.1.3 Medical History Full Analysis Population (FAP)

Table 14.1.4 Extent of Exposure to Study Drug Full Analysis Population (FAP)

Table 14.1.5 Treatment Compliance Full Analysis Population (FAP)

Table 14.1.6.1 Prior Medication Full Analysis Population (FAP)

Table 14.1.6.2 Concomitant Medication During Treatment with Study Drug Full Analysis Population (FAP)

Table 14.1.6.3 Concomitant Medication Following End of Treatment with Study Drug Full Analysis Population (FAP)

Table 14.2.1.1.1.1 Change from Baseline in the Weekly Mean of the Daily 24 Hour Pain Intensity (NRS) Scores over time

– Descriptive Statistics Over All Patients Full Analysis Population (FAP)

Table 14.2.1.1.1.2 Change from Baseline in the Weekly Mean of the Daily 24 Hour Pain Intensity (NRS) Scores over time

– Descriptive Statistics for Stage 1 Full Analysis Population (FAP)

Table 14.2.1.1.1.3 Change from Baseline in the Weekly Mean of the Daily 24 Hour Pain Intensity (NRS) Scores over time

– Descriptive Statistics for Stage 2 Full Analysis Population (FAP)

Table 14.2.1.1.2.1 Change from Baseline in the Weekly Mean of the Daily 24 Hour Pain Intensity (NRS) at Week 8 - Primary Efficacy Analysis (MMRM with MNAR Pattern Mixture Modeling) Over All Patients Full Analysis Population (FAP)

Table 14.2.1.1.2.2 Change from Baseline in the Weekly Mean of the Daily 24 Hour Pain Intensity (NRS) at Week 8 - Primary Efficacy Analysis (MMRM with MNAR Pattern Mixture Modeling) for Stage 1 Full Analysis Population (FAP)

Table 14.2.1.1.2.3 Change from Baseline in the Weekly Mean of the Daily 24 Hour Pain Intensity (NRS) at Week 8 - Primary Efficacy Analysis (MMRM with MNAR Pattern Mixture Modeling) for Stage 2 Full Analysis Population (FAP)

Table 14.2.1.1.3.1 Change from Baseline in the Weekly Mean of the Daily 24 Hour Pain Intensity (NRS) at Week 8 - Primary Efficacy Analysis (MMRM with MNAR Pattern Mixture Modeling) Over All Patients Per-Protocol Population (PP)

Table 14.2.1.1.3.2 Change from Baseline in the Weekly Mean of the Daily 24 Hour Pain Intensity (NRS) at Week 8 - Primary Efficacy Analysis (MMRM with MNAR Pattern Mixture Modeling) for Stage 1 Per-Protocol Population (PP)

Table 14.2.1.1.3.3 Change from Baseline in the Weekly Mean of the Daily 24 Hour Pain Intensity (NRS) at Week 8 - Primary Efficacy Analysis (MMRM with MNAR Pattern Mixture Modeling) for Stage 2 Per-Protocol Population (PP)

Table 14.2.1.1.4.1 Change from Baseline in the Weekly Mean of the Daily 24 Hour Pain Intensity (NRS) at Week 8 – MMRM Analysis on Observed Data Over All Patients Full Analysis Population (FAP)

Table 14.2.1.1.4.2 Change from Baseline in the Weekly Mean of the Daily 24 Hour Pain Intensity (NRS) at Week 8 – MMRM Analysis on Observed Data For Stage 1 Full Analysis Population (FAP)

Table 14.2.1.1.4.3 Change from Baseline in the Weekly Mean of the Daily 24 Hour Pain Intensity (NRS) at Week 8 – MMRM Analysis on Observed Data For Stage 2 Full Analysis Population (FAP)

Table 14.2.1.1.5.1 Change from Baseline in the Weekly Mean of the Daily 24 Hour Pain Intensity (NRS) at Week 8 - Sensitivity Analysis 1: MMRM with MAR Pattern Mixture Modeling Over All Patients Full Analysis Population (FAP)

Table 14.2.1.1.5.2 Change from Baseline in the Weekly Mean of the Daily 24 Hour Pain Intensity (NRS) at Week 8 - Sensitivity Analysis 1: MMRM with MAR Pattern Mixture Modeling for Stage 1 Full Analysis Population (FAP)

Table 14.2.1.1.5.3 Change from Baseline in the Weekly Mean of the Daily 24 Hour Pain Intensity (NRS) at Week 8 - Sensitivity Analysis 1: MMRM with MAR Pattern Mixture Modeling for Stage 2 Full Analysis Population (FAP)

Table 14.2.1.1.6.1 Change from Baseline in the Weekly Mean of the Daily 24 Hour Pain Intensity (NRS) at Week 8 - Sensitivity Analysis 2: MMRM with MNAR Placebo Based Pattern Mixture Modeling Over All Patients Full Analysis Population (FAP)

Table 14.2.1.1.6.2 Change from Baseline in the Weekly Mean of the Daily 24 Hour Pain Intensity (NRS) at Week 8 - Sensitivity Analysis 2: MMRM with MNAR Placebo Based Pattern Mixture Modeling For Stage 1 Full Analysis Population (FAP)

Table 14.2.1.1.6.3 Change from Baseline in the Weekly Mean of the Daily 24 Hour Pain Intensity (NRS) at Week 8 - Sensitivity Analysis 2: MMRM with MNAR Placebo Based Pattern Mixture Modeling For Stage 2 Full Analysis Population (FAP)

Table 14.2.1.1.7.1 Change from Baseline in the Weekly Mean of the Daily 24 Hour Pain Intensity (NRS) at Week 8 - Sensitivity Analysis 3: Single Imputation BOCF/LOCF Over All Patients Full Analysis Population (FAP)

Table 14.2.1.1.7.2 Change from Baseline in the Weekly Mean of the Daily 24 Hour Pain Intensity (NRS) at Week 8 - Sensitivity Analysis 3: Single Imputation BOCF/LOCF For Stage 1 Full Analysis Population (FAP)

Table 14.2.1.1.7.3 Change from Baseline in the Weekly Mean of the Daily 24 Hour Pain Intensity (NRS) at Week 8 - Sensitivity Analysis 3: Single Imputation BOCF/LOCF For Stage 2 Full Analysis Population (FAP)

Table 14.2.1.1.8 Change from Baseline in the Weekly Mean of the Daily 24 Hour Pain Intensity (NRS) – Descriptive Statistics by Primary OA Joint Full Analysis Population (FAP)

Table 14.2.1.2.1 Responder Analysis of Percentage Improvement from Baseline in the Weekly Mean of the Daily 24 Hour Pain Intensity (NRS) Scores at Week 8 Full Analysis Population (FAP)

Table 14.2.1.2.2 Responder Analysis of Percentage Improvement from Baseline in the Weekly Mean of the Daily 24 Hour Pain Intensity (NRS) Scores at Week 8 by Primary OA Joint Full Analysis Population (FAP)

Table 14.2.2.1.1 Change from Baseline in the WOMAC Index Score Over Time – Descriptive Statistics Full Analysis Population (FAP)

Table 14.2.2.1.2 Change from Baseline in the WOMAC Index Total Score – MMRM Analysis Full Analysis Population (FAP)

Table 14.2.2.1.3 Change from Baseline in the WOMAC Index Total Score Over Time by Primary OA Joint Full Analysis Population (FAP)

Table 14.2.2.2.1 Change from Baseline in the WOMAC Index Pain Intensity Subscale Score Over Time – Descriptive Statistics Full Analysis Population (FAP)

Table 14.2.2.2.2 Change from Baseline in the WOMAC Index Pain Intensity Subscale Score – MMRM Analysis Full Analysis Population (FAP)

Table 14.2.2.2.3 Change from Baseline in the WOMAC Index Total Score Over Time by Primary OA Joint Full Analysis Population (FAP)

Table 14.2.2.3.1 Change from Baseline in the WOMAC Index Stiffness Intensity Subscale Score Over Time – Descriptive Statistics Full Analysis Population (FAP)

Table 14.2.2.3.2 Change from Baseline in the WOMAC Index Stiffness Intensity Subscale Score – MMRM Analysis Full Analysis Population (FAP)

Table 14.2.2.3.3 Change from Baseline in the WOMAC Index Stiffness Intensity Subscale Score Over Time by Primary OA Joint Full Analysis Population (FAP)

Table 14.2.2.4.1 Change from Baseline in the WOMAC Index Function Intensity Subscale Score Over Time – Descriptive Statistics Full Analysis Population (FAP)

Table 14.2.2.4.2 Change from Baseline in the WOMAC Index Function Intensity Subscale Score – MMRM Analysis Full Analysis Population (FAP)

Table 14.2.2.4.3 Change from Baseline in the WOMAC Index Function Intensity Subscale Score Over Time by Primary OA Joint Full Analysis Population (FAP)

Table 14.2.3 Patient Global Impression of Change (PGIC) at Day 57/ET Full Analysis Population (FAP)

Table 14.2.4 Average Daily Use of Rescue Medication for Target Joint Pain Full Analysis Population (FAP)

Table 14.2.5 Proportion of patients withdrawing from treatment due to lack of analgesic efficacy Full Analysis Population (FAP)

Table 14.3.1.1 Overall Summary of Adverse events
Safety Population (SAF)

Table 14.3.1.2 Summary of Treatment Emergent Adverse Events (TEAEs) by System Organ Class and Preferred Term Safety Population (SAF)

Table 14.3.1.3 Summary of Treatment-Related Treatment Emergent Adverse Events (TEAEs) by System Organ Class and Preferred Term Safety Population (SAF)

Table 14.3.1.4 Summary of Treatment Emergent Adverse Events (TEAEs) by System Organ Class, Preferred Term and Maximum Severity Safety Population (SAF)

Table 14.3.1.5 Summary of Treatment Emergent Adverse Events (TEAEs) occurring in $\geq 5\%$ of patients in at least one treatment group by System Organ Class and Preferred Term Safety Population (SAF)

Table 14.3.1.6 Summary of Treatment-Related Treatment Emergent Adverse Events (TEAEs) occurring in $\geq 5\%$ of patients in at least one treatment group by System Organ Class and Preferred Term Safety Population (SAF)

Table 14.3.1.7 Summary of Serious Treatment Emergent Adverse Events (TEAEs) by System Organ Class and Preferred Term Safety Population (SAF)

Table 14.3.1.8 Summary of Treatment Emergent Adverse Events (TEAEs) leading to treatment discontinuation by System Organ Class and Preferred Term Safety Population (SAF)

Table 14.3.1.9 Summary of Non-Treatment Emergent Adverse Events (NTEAEs) Following Last Dose of Study Drug by System Organ Class and Preferred Term Safety Population (SAF)

Table 14.3.2.1 Listing of Deaths Safety Population (SAF)

Table 14.3.2.2 Listing of Treatment-Emergent Serious Adverse Events (SAEs) Safety Population (SAF)

Table 14.3.2.3 Listing of Non Treatment-Emergent Serious Adverse Events (SAEs) Safety Population (SAF)

Table 14.3.2.4 Listing of Treatment-Emergent Adverse Events (TEAEs) leading to study drug discontinuation, dose reduction or dose interruption Safety Population (SAF)

Table 14.3.4.1.1 Summary of Hematology Quantitative Laboratory Parameters Safety Population (SAF)

Table 14.3.4.1.2 Shift Table of L/N/H Classification for Hematology Laboratory Parameters Safety Population (SAF)

Table 14.3.4.1.3 Shift Table of Incidence of Markedly Abnormal Results for Hematology Laboratory Parameters Safety Population (SAF)

Table 14.3.4.1.4 Listing of Patients with at Least One Markedly Abnormal Hematology Laboratory Parameter Safety Population (SAF)

Table 14.3.4.2.1 Summary of Sodium Laboratory Tests Safety Population (SAF)

Table 14.3.4.2.2 Categorical Summary of Sodium Laboratory Tests Safety Population (SAF)

Table 14.3.4.2.3 Listing of Patients with at Least One Sodium Result $> 146 \text{ mmol/L}$ or $> 150 \text{ mmol/L}$ Safety Population (SAF)

Table 14.3.4.3.1 Summary of Liver Function Tests Safety Population (SAF)

Table 14.3.4.3.2 Shift Tables of Categorical Classification for Liver Function Tests – AST Safety Population (SAF)

Table 14.3.4.3.3 Shift Tables of Categorical Classification for Liver Function Tests – ALT Safety Population (SAF)

Table 14.3.4.3.4 Shift Tables of Categorical Classification for Liver Function Tests – Total Bilirubin Safety Population (SAF)

Table 14.3.4.3.5 Listing of Patients with at AST > 3 ULN, ALT > 3 ULN or Total Bilirubin > 1.5 ULN Safety Population (SAF)

Table 14.3.4.4.1 Summary of Other Quantitative Serum Chemistry Laboratory Parameters Safety Population (SAF)

Table 14.3.4.4.2 Shift Table of L/N/H Classification for Other Serum Chemistry Laboratory Parameters Safety Population (SAF)

Table 14.3.4.4.3 Shift Table of Incidence of Markedly Abnormal Results for Other Serum Chemistry Laboratory Parameters Safety Population (SAF)

Table 14.3.4.4.4 Listing of Patients with at Least One Markedly Abnormal Other Serum Chemistry Parameter Safety Population (SAF)

Table 14.3.4.5.1 Summary of Systolic Blood Pressure During the Study Safety Population (SAF)

Table 14.3.4.5.2 Shift Table of Maximum L/N/H Classification for Systolic Blood Pressure During the Study Safety Population (SAF)

Table 14.3.4.5.3 Shift Table of Minimum L/N/H Classification for Systolic Blood Pressure During the Study Safety Population (SAF)

Table 14.3.4.6.1 Summary of Diastolic Blood Pressure During the Study Safety Population (SAF)

Table 14.3.4.6.2 Shift Table of Maximum L/N/H Classification for Diastolic Blood Pressure During the Study Safety Population (SAF)

Table 14.3.4.6.3 Shift Table of Minimum L/N/H Classification for Diastolic Blood Pressure During the Study Safety Population (SAF)

Table 14.3.4.7.1 Summary of Heart Rate During the Study Safety Population (SAF)

Table 14.3.4.7.2 Shift Table of Maximum L/N/H Classification for Heart Rate During the Study Safety Population (SAF)

Table 14.3.4.7.3 Shift Table of Minimum L/N/H Classification for Heart Rate During the Study Safety Population (SAF)

Table 14.3.4.8.1 Summary of Temperature During the Study Safety Population (SAF)

Table 14.3.4.8.2 Shift Table of Maximum L/N/H Classification for Temperature During the Study Safety Population (SAF)

Table 14.3.4.8.3 Shift Table of Minimum L/N/H Classification for Temperature During the Study Safety Population (SAF)

Table 14.3.4.9.1 Incidence of Clinically Notable Vital Sign Abnormalites for SBP, DBP, Respiratory Rate and Heart Rate Safety Population (SAF)

Table 14.3.4.9.2 Listing of Patients with Clincally Notable Vital Sign Abnormalities for SBP, DBP, Respiratory Rate or Heart Rate Safety Population (SAF)

Table 14.3.4.10.1 ECG Results Safety Population (SAF)

Table 14.3.4.10.2 Shift Table of Investigator Interpretation of ECG Results over the study Safety Population (SAF)

Table 14.3.4.10.3 Listing of Clinically Significant Abnormal ECG Results over the study Safety Population (SAF)

